### 5. GENERAL METHODOLOGY AND CONVENTIONS

This is an open-label dose escalation study and no interim analysis or blinding is planned for this study. The final analysis will be conducted after the last subject last visit (LSLV).

#### 5.1. Statistical Hypotheses

There are no statistical hypotheses. The emphasis of the final analyses will be on estimation of study endpoints.

#### 5.2. Statistical Decision Rules

##### 5.2.1. Part 1 (MTD Finding)

**In Part 1**, patients will participate in a dose escalation phase aimed at estimating the MTD. The sample size for this component of the study will vary depending on the number of DLTs observed. It is anticipated that the maximum sample size of approximately upto 92 patients are expected to be enrolled in Part 1 of the study at 3 - 6 sites. The actual number of patients enrolled will depend upon tolerability and the number of dose levels required to identify the MTD.

The minimum and maximum sample sizes after which Part 1 can be stopped and MTD declared are approximately 6-12 and approximately 92 patients, respectively. As for the number of patients treated at each dose, it is expected that the typical number will be 1 to 4 patients for the doses actually studied. However, since variable cohort size is allowed, the actual number of patients treated at each dose will vary from 1 to 12.

The following table shows the probability of escalating to the next dose level for a range of underlying true DLT rates. For example, for a cohort size of n=3 and for a DLT that occurs in 10% of patients, there is a greater than 90% probability of escalating. Conversely, for a DLT that occurs with a rate of 70%, the probability of escalating is 3%. It is assumed that dose escalation occurs with either 0/3 or 1/6 patients with DLTs.

Probability of Escalating Dose									
True underlying DLT rate	10%	20%	30%	40%	50%	60%	70%	80%	90%
Probability of escalating	0.91	0.71	0.49	0.31	0.17	0.08	0.03	0.009	0.001

### 5.2.2. Part 2 (Dose Expansion)

In **Part 2** the maximum sample sizes for each tumor indication (ie, TNBC, CRC and NSCLC) will be of n=10 to 20 evaluable patients. Enrollment of patients in one indication may be discontinued if minimal or no anti-tumor activity (eg 0 or 1 response) is observed in the first 10 evaluable patients for that indication.

[figure not shown]
### 5.2.3. Sample Size Determination

The exact sample size for the dose escalation design in Part 1 cannot be specified in advance due to the dynamic features of mTPI.

*Assuming a non-informative prior (ie, Jeffrey's prior) if 1 out of 10 patients have tumor response, this would predict a posterior probability (Beta-Binomial) equal to 0.93 that the true response is inferior to 30%. On the other hand, if 7 out of 20 patients have tumor response, this would predict a posterior probability equal to 0.70 that the true response is not inferior to 30% and a posterior probability equal to 0.05 (5%) that the true response is inferior to 20%. In addition, posterior probabilities may be calculated by using informative priors based on the antitumor activity that may be observed during Part 1 (eg 2 out of 3 TNBC patients experience tumor response in Part 1). These posterior probabilities will be assessed for each indication during Part 2 when at least the first 10 Pts are enrolled in that indication. Posterior Probabilities >0.75 of an ORR <20% (eg, 0,1 out of 10; 0,1,2 out of 16) may provide evidence of no substantial anti-tumor activity for that indication.*

[Reference Source: Protocol Section 9.3]

CCI

Unless otherwise specified, the baseline value is defined as the value collected at the time closest to, but prior to, the start of study drug administration in the first cycle (in general C1D1). All data will be categorized based on the scheduled visit at which it was collected. These visit designators are predefined values that appear as part of the visit tab in the eCRF.

### **5.3.1. Analyses for Time to Event Data**

Time-to-event endpoints will be summarized using the Kaplan-Meier method and displayed graphically when appropriate. Median event times and 2-sided 95% confidence intervals for each time-to-event endpoint (Brookmeyer and Crowley, 1982) will be provided.

### **5.3.2. Analyses for Binary Data**

The rates of binary endpoints will be provided along with the corresponding 2-sided 95% confidence intervals using an exact method.

### **5.3.3. Analyses for Continuous Data**

Descriptive statistics, such as the mean, standard deviation, coefficient of variation, median, minimum, and maximum values, will be provided for continuous endpoints.

### **5.3.4. Analyses for Pharmacokinetic Data**

Blood samples for PK analysis of PF-06671008 will be taken according to the Schedule of Activities given in the protocol. PK parameters listed in [Section 3.2](#) will be derived from the concentration-time data using non compartmental analysis as follows:

Parameter	Definition	Method of Determination
$AUC_{sd,\tau}$	Area under the concentration-time profile from time zero to the time $\tau$ , the dosing interval	Linear/Log trapezoidal method
$AUC_{ss,\tau}$	Area under the concentration-time profile during one dosing interval, $\tau$ , at steady state	Linear/Log trapezoidal method
$AUC_{inf}$	Area under the concentration-time profile from time zero extrapolated to infinite time	$AUC_{(0-t_{last})} + (C_{last}^* / kel)$ , where $C_{last}^*$ is the predicted serum concentration at the last quantifiable time point estimated from the log-linear regression analysis.
$C_{max}$	Maximum observed concentration	Observed directly from data
$C_{max,ss}$	Maximum observed concentration at steady state	Observed directly from data
$C_{min,ss}$	Minimum observed concentration at steady state	Observed directly from data
$T_{max}$	Time for $C_{max}$	Observed directly from data
$T_{max,ss}$	Time for $C_{max}$ at steady state	Observed directly from data
$t_{1/2}$	Terminal elimination half-life	$\log(2) / kel$ , where $kel$ is the terminal phase rate constant calculated by a linear regression of the log-linear concentration-time curve. Only those data points judged to describe the terminal log-linear decline will be used in the regression.
CL	Clearance for IV administration	Dose/ $AUC_{inf}$ for dose 1; Dose/ $AUC_{\tau}$ for dose 4
CL/F	Apparent clearance for SC administration	Dose/ $AUC_{inf}$ for dose 1; Dose/ $AUC_{\tau}$ for dose 4
$V_{ss}$	Volume of distribution at steady state for IV administration	$CL \times MRT$
$V_{ss}/F$	Apparent volume of distribution at steady state for SC administration	$CL/F \times MRT$
$R_{ac}$	Observed accumulation ratio	$AUC_{dose\ 4, \tau} / AUC_{dose\ 1, \tau}$

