11. **Pregnancy Test:** For female patients of childbearing potential, a serum or urine pregnancy test, with sensitivity of at least 25 mIU/mL will be performed on two occasions prior to starting study treatment – once at the start of screening and once on C1D1 immediately before investigational product administration. Pregnancy tests will also be routinely repeated at every cycle during the active treatment period, at the end of study treatment and additional whenever one menstrual cycle is missed or when potential pregnancy is otherwise suspected. Additional pregnancy tests may also be undertaken if requested by institutional review board (IRB) or if required by local regulations.
12. **Triplet 12-Lead ECG:** Triplet 12-lead ECGs to be collected before dosing and at 24 hours post the Cycle 1 Day 1 and Cycle 2 Day 1 PF-06671008 injections. At each time point, three consecutive 12-lead ECGs will be performed approximately 2 minutes apart to determine mean QTcF interval. When coinciding with blood sample draws for pharmacokinetics (PK), ECG assessment should be performed prior to blood sample collection, such that the blood sample is collected at the nominal time. If the mean QTcF is prolonged (>500 msec), the ECGs should be re-evaluated by a qualified person at the institution for confirmation. Additional triplet ECGs may be performed as clinically indicated.
13. **Registration:** Patient enrollment number and dose level allocation provided by Pfizer Inc. Registration should occur before any other Day 1 activities are performed.
14. **Study Treatment:** PF-06671008 will be administered once every 7 days as a subcutaneous injection.
15. **Injection Site Tolerability Assessment:** Assessment of each injection should be conducted for at least 1 hour following each treatment administration in Cycle 1. In addition, an assessment should be performed 24 hours (± 1 hour) after the Cycle 1 Day 1 dose. Injection site tolerability assessments should continue after each dosing visit in Cycle 2 and beyond, only if injection site pain or injection site reaction (ISR) characteristics continue to persist. The assessments should continue at regularly scheduled visits until the symptoms resolve.

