5.1. Allocation to Treatment

Patient enrollment number and dose level allocation will be performed by the sponsor after patients have given their written informed consent and have completed the necessary baseline assessments. The site staff will email a complete Registration Form to the designated sponsor study team member. The sponsor will assign a patient identification number documenting patient enrollment. IV and SC routes of administration will be enrolled in parallel. Patients will be allocated to a dose escalation cohort and route of administration based on the sequential available slots.

No patient shall receive investigational product until the investigator or designee has received the following information in writing from the sponsor:

- confirmation of the patient's enrollment;
- specification of the dose level and route of administration for that patient and;
- permission to proceed with dosing the patient.

The sponsor or designee will notify the other sites of the inclusion of a new patient, and will inform study sites about the next possible enrollment date.

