9.5. Analysis of Pharmacokinetics CCI

9.5.1. Analysis of Pharmacokinetics

PK parameters for single dose including the maximum concentration (C_{max}), time to maximum concentration (T_{max}), and area under the concentration versus time curve (AUC_{last} , $AUC_{sd,\tau}$) will be estimated using non-compartmental analysis. PK parameters for multiple dose (assuming steady state is achieved) including the maximum concentration ($C_{ss,max}$), time to maximum concentration ($T_{ss,max}$), and area under the concentration versus time curve ($AUC_{ss,\tau}$) will be estimated using non-compartmental analysis. If data permit or if considered appropriate, area under the concentration versus time curve to infinity (AUC_{inf}), terminal elimination half-life ($t_{1/2}$), clearance (CL) for IV administration or apparent clearance (CL/F) for SC administration, volume of distribution at steady state (V_{ss}) for IV administration or apparent volume of distribution at steady state (V_{ss}/F) for SC administration, and accumulation ratio ($R_{ac} = AUC_{ss,\tau}/AUC_{sd,\tau}$) will be also estimated. Actual sample collection times will be used for the parameter calculations. The PK parameters will be summarized descriptively by dose, cycle, dosing day and route of administration.

PF-06671008 concentrations will be summarized descriptively (n, mean, SD, coefficient of variation(CV), median, minimum, maximum, geometric mean and its associated CV) by dose, cycle, day and nominal time. Median profiles of the concentration-time data will be plotted by dose, cycle and day (single dose and steady state) using nominal times, for dosing intervals with full PK profile. Median profiles will be presented on both linear-linear and log-linear scales.

Dose normalized AUC_{inf} (AUC_{τ} at steady state), AUC_{last} and C_{max} will be plotted against dose (using a logarithmic scale) by cycle and dosing day. These plots will include individual patient values and the geometric means for each dose level. These plots will be used to help understand the relationship between the PK parameters and dose.

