### 3.2. Secondary Endpoint (s)

- *Adverse Events as characterized by type, frequency, severity (as graded by National Cancer Institute Common Terminology Criteria for Adverse Events (NCI CTCAE) v.4.03) timing, seriousness, and relationship to study therapy;*
- *Laboratory abnormalities as characterized by type, frequency, severity (as graded by NCI CTCAE v.4.03) and timing;*
- *Vital sign abnormalities;*
- Pharmacokinetic parameters of PF-06671008 Single Dose (SD) -  $C_{max}$ ,  $T_{max}$ ,  $AUC_{sd,\tau}$ ,  $t_{1/2}$ ,  $AUC_{inf}$ , and CL for intravenous (IV) administration or apparent clearance (CL/F) for subcutaneous (SC) administration as data permit. Multiple Dose (MD) (assuming steady state is achieved) -  $C_{max,ss}$ ,  $T_{max,ss}$ ,  $AUC_{ss,\tau}$ ,  $t_{1/2}$ ,  $C_{min,ss}$ , CL for IV or CL/F for SC, volume of distribution ( $V_{ss}$ ) for IV or apparent volume of distribution at steady state ( $V_{ss}/F$ ) for SC, and  $R_{ac}$  ( $AUC_{ss,\tau}/AUC_{sd,\tau}$ ) as data permit;
- Incidence and titers of anti-drug antibodies (ADA) and neutralizing antibodies against PF-06671008;
- *Objective response, as assessed using the RECIST version 1.1 – Part 1 only;*
- *Progression Free Survival (PFS) and Overall Survival (OS) – Part 2 only.*

CCI

CCI

Covariates may also be considered when exploring QTc and PK relationship.

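### SAP 5.3.4 computes the subcutaneous Vss/F as CL/F x MRT with MRT undefined and no correction for absorption time, so the formula does not return Vss/F

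*SAP*

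**What the plan says.** SAP 5.3.4 states that the PK parameters "will be derived from the concentration-time data using non compartmental analysis as follows". The table that follows uses one construction for both routes: Vss for IV is CL x MRT, and "Apparent volume of distribution at steady state for SC administration" is CL/F x MRT. The clearance term, for either route, is "Dose/ $AUC_{inf}$ for dose 1; Dose/ $AUC_{\tau}$ for dose 4". MRT has no row in the table and no definition elsewhere in the readable protocol or SAP. No subtraction of absorption time (SC) or infusion time (IV) is stated.

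The parameter is a named secondary endpoint. SAP 3.2 lists "apparent volume of distribution at steady state ( $V_{ss}/F$ ) for SC" under multiple dose, as data permit, and Protocol 2.2 matches it. Protocol 9.5.1 also makes it conditional on the data, and says "The PK parameters will be summarized descriptively by dose, cycle, dosing day and route of administration".

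On design, the SC Schedule of Activities (footnote 14) says "PF-06671008 will be administered once every 7 days as a subcutaneous injection". Protocol 5.1 says "Patients will be allocated to a dose escalation cohort and route of administration based on the sequential available slots". No patient is described as giving both an IV and an SC profile.

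**The concern.** CL x MRT equals Vss only when MRT is the disposition residence time, meaning the mean time a molecule spends in the body once it has reached the circulation. After an IV dose, AUMC/AUC gives this, apart from half the infusion time. After an SC dose, AUMC/AUC also counts the time spent leaving the injection site. Carrying the IV formula over to SC therefore adds an absorption term to something labelled a volume of distribution.

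An SC profile alone does not show how much of its MRT is absorption. Because each patient is allocated to one route, that patient has no IV reference profile from which MAT could be obtained and subtracted. An analyst who follows SAP 5.3.4 literally will report a value that is not the named endpoint, and part of what looks like volume will be slow absorption.

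**Working it through.** The plan gives no MRT, MAT, half-life or Vss, so there is no figure to reproduce. The check is algebra plus a range over assumed half-lives.

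**Inputs from the documents.** Vss/F = CL/F x MRT; CL/F = Dose/AUCinf (dose 1) or Dose/AUCtau (dose 4), both SAP 5.3.4. Dosing interval tau = 7 days, SC Schedule of Activities. IV infusion 1 hour (Cohort 1) or 2 hours (Cohort 2 onward), IV Schedule of Activities footnote 14.

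**Assumed.** One compartment with first-order absorption; elimination half-life 3, 7 or 14 days; absorption half-life 1, 2 or 3 days.

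**Step 1: the bias.** After SC dosing, AUMC/AUC = MRT(disposition) + MAT. Hence

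(CL/F) x (AUMC/AUC) = Vss/F + (CL/F) x MAT,

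and the ratio to the true value is 1 + MAT/MRT(disposition). F cancels. In this model MRT(disposition) = elimination half-life/ln 2 and MAT = absorption half-life/ln 2, so the ratio is 1 + (absorption half-life/elimination half-life).

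Example, elimination 7 days and absorption 1 day: MRT(disposition) = 10.10 d, MAT = 1.44 d, observed MRT = 11.54 d, ratio = 11.54/10.10 = 1.14.

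**Step 2: full-form MRT.** The same ratios hold for a single dose (AUMCinf/AUCinf) and at steady state with (AUMCtau + tau x AUC from tau to infinity)/AUCtau. Numerical integration agrees with the algebra.

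| Elimination half-life | Absorption 1 d | 2 d | 3 d |
|---|---|---|---|
| 3 d | 1.33 | 1.67 | 2.00 |
| 7 d | 1.14 | 1.29 | 1.43 |
| 14 d | 1.07 | 1.14 | 1.21 |

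A wider grid (elimination 1 to 7 days, absorption 0.25 to 4 days) runs from 1.04 to 5.00.

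**Step 3: truncated MRT at dose 4.** The SAP does not exclude AUMCtau/AUCtau taken over the 7-day interval. That quantity cannot exceed 7 days, however long the true residence time. With elimination 7 d and absorption 1 d, scaled so that true Vss/F = 1, the fourth weekly dose gives AUCtau = 9.36 and AUMCtau/AUCtau = 3.41 d, so the product is 3.41/9.36 = 0.36. Over the nine pairs in the table the ratio runs from 0.24 to 0.80, below 1 each time. The sign of the error therefore depends on a definition the SAP does not give. With shorter elimination half-lives even the truncated form can exceed 1: at steady state it is 1.20 for elimination 1 d and absorption 0.25 d.

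**Step 4: the IV formula.** Ignoring infusion time inflates IV Vss by the factor 1 + (T/2) x kel, where T is the infusion time. For T of 1 or 2 hours and elimination half-lives of 1 to 7 days this is 0.2% to 2.9%. The problem lies mainly with SC.

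**Step 5: does the obvious substitute work?** Vz/F = (CL/F)/kel uses quantities already in SAP 5.3.4. The SC sampling times are not readable, so suppose the slope is fitted to days 3, 5 and 7 after dose 1. For elimination 3 d with absorption 3 d, Vz/F is 2.70 times the true volume using the predicted last concentration, as the SAP specifies (2.77 with the observed one). For 7 d/2 d, 7 d/3 d and 14 d/3 d concentrations are still rising over that window and kel cannot be estimated. Vz/F needs an adequate terminal slope to be reported at all.

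**The case against.** The strongest reply is that the upward bias comes from a definition of MRT the SAP never states. Vss/F is listed under multiple dose, where CL/F uses AUCtau, and a truncated MRT there can make the value too low. That stands: a reader might infer that every SC Vss/F will be overstated, and the documents do not support it. It does not rescue the formula, because neither form returns Vss/F and the SAP states no correction that would.

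A reader might also infer that absorption time is what prevents comparison with the IV Vss. It is not the only bar. A correct Vss/F still carries 1/F, and the readable text gives no F; Protocol 1.5.2 says only that SC exposure is projected to be lower than IV at the same dose. SAP 6.3.2 lists both parameters in one row of a table assigning summary statistics, but no IV-versus-SC comparison of volumes is planned.

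Third, it is tempting to say the error could steer the choice of route or seed the population PK model. No text says so. Protocol 3.1 ties dropping a route to emerging clinical and safety data, the MTD rests on DLTs, and neither document uses the non-compartmental Vss/F as a starting value.

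Finally, the parameter is conditional on the data, so the analyst may decline to report it. That lowers the stakes but leaves the formula as it is.

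**Conclusion.** The point holds in limited form. As written, SAP 5.3.4 does not yield the SC Vss/F that SAP 3.2 and Protocol 2.2 name as a secondary endpoint, and a patient's own SC data cannot supply the missing correction. With a full-form MRT the error is upward by 1 + MAT/MRT(disposition), which is algebra and does not depend on F. The size rests wholly on assumed half-lives and could be a few percent or a doubling. With a truncated MRT at dose 4 the error may be downward, so a fixed direction should not be claimed.

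The reach is one descriptive secondary parameter. DLT, MTD, response, AUC, Cmax and CL/F do not use MRT and are unaffected. It should be corrected before analysis because it is a wrong derivation of a named endpoint, not because a trial decision depends on it.

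**What to change.** In SAP 5.3.4 and 6.3.2, and in the endpoint lines of SAP 3.2 and Protocol 2.2 (with the Protocol Summary):

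- **IV:** report Vss for IV cohorts only. Add an MRT row: AUMCinf/AUCinf at dose 1; (AUMCtau + tau x AUC from tau to infinity)/AUCtau at dose 4, if steady state is reached; each minus half the infusion time.
- **SC:** replace Vss/F with Vz/F = (CL/F)/kel, reported only when the terminal slope is adequately characterised. Footnote that it is a terminal-phase volume, still carries 1/F, and is invalid if absorption is slower than elimination, because kel then reflects absorption.
- **SC Vss/F, if still wanted:** take it only from the population PK model, if that model is run. Protocol 9.5.2 and SAP 6.5 leave it optional.

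The cost is wording and one derived variable, with no new samples. The downside is that Vz/F is a different parameter from Vss/F and may not be estimable in some patients, so the SC table may have gaps.

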In addition, PF-06671008 will also be administered in cohorts as a weekly SC injection in 21-day cycles with a starting dose equal to the dose level selected as the IV Dose Prime (See Section [Evaluation of a Priming Dose](#)). Dose escalation cohorts with PF-06671008 SC administration will be evaluated independently in parallel with dose escalation cohorts evaluating PF-06671008 IV administration (See Section [Criteria for Dose Escalation](#)). For cohorts where a SC route of administration will be evaluated, there will also be a minimum 72-hour interval between the first dose administered to each of the initial patients (ie, patients contributing to initial DLT evaluation) enrolled at a new dose level due to the unknown time course of possible cytokine release. All patients who will be dosed subcutaneously will be observed in-patient for at least 48 hours after the first dose on Cycle 1 Day 1 (C1D1). Additional in-patient observation for subsequent cycles beyond C1D1 may be considered based on the investigator's discretion and should be discussed with Pfizer. Evaluation of either the IV or SC route of administration may be discontinued based on emerging clinical and safety data.

In the event study treatment administration is delayed due to toxicities during Cycle 1, the day when the patient receives their 4th dose of study drug will be counted as Day 1 of Cycle 2.

Treatment with investigational product will continue until either disease progression, patient refusal, or unacceptable toxicity occurs, whichever is earliest, unless the investigator and medical monitor agree to treatment beyond disease progression based on individual benefit/risk assessments.

Figure 3. Overall Study Design

The proposed doses, schedule(s), and PK time points may be reconsidered and amended during the study based on the emerging safety and PK data.

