In addition, observation of a confirmed CRS event that meets the above qualifications following later infusions (ie, after Cycle 1 Day 1) or CRS events that are approaching the limit of tolerability may prompt the investigators and sponsor to include evaluation of a Dose Prime for subsequent cohorts.

After confirmation of the safety of Dose Prime, the treatment schedule will implement the inclusion of the fixed priming dose as the first dose (C1D1) followed by a second dose (C1D8) that will continue to be escalated in subsequent cohorts following an mTPI method in cohorts of 2-4 patients. After the MTD has been established, the priming dose may potentially be further verified in connection to the established MTD/RP2D, including consideration of more than one priming step, if indicated, using information from all patients who were included in the initial priming dose determination as well as those enrolled in subsequent dosing cohorts.

The primary DLT observation period for cohorts that include Dose Prime will be 21 days following the first dose (C1D1). The dose escalation should a Dose Prime be instituted is depicted in Figure 4.

For cohorts instituting a Dose Prime, there will be a 72 hour observation period between the first dose administered to each of the initial patients enrolled (ie, patients contributing to initial DLT evaluation) at a new dose level. In addition to in-patient observation following the C1D1 dose, patients enrolled in cohorts instituting a Dose Prime must also undergo in-patient observation for at least 24 hours (for cohorts where PF-06671008 will be administered IV) or 48 hours (for cohorts where PF-06671008 will be administered SC) following the C1D8 dose.

Figure 4. Study Schematic Should Dose Prime Be Explored

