The observed accumulation ratio and the linearity ratio will be summarized descriptively. Each will be analyzed after natural log transformation using a one-way analysis of variance with a single term for dose. The means and 90% confidence intervals (CIs) obtained from the model will be back-transformed to provide means and 90% CIs for the accumulation and linearity ratios for each dose.

Trough concentrations will be plotted for the first 2 cycles using a box-whisker plot by cycle and day within cycle in order to assess the attainment of steady state.

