*In addition, observation of a confirmed CRS event that meets the above qualifications following later infusions (ie, after Cycle 1 Day 1) or CRS events that are approaching the limit of tolerability may prompt the investigators and sponsor to include evaluation of a Dose Prime for subsequent cohorts.*

*After confirmation of the safety of Dose Prime, the treatment schedule will implement the inclusion of the fixed priming dose as the first dose (C1D1) followed by a second dose (C1D8) that will continue to be escalated in subsequent cohorts following an mTPI method in cohorts of 2-4 patients. After the MTD has been established, the priming dose may potentially be further verified in connection to the established MTD/RP2D, including consideration of more than one priming step, if indicated, using information from all patients who were included in the initial priming dose determination as well as those enrolled in subsequent dosing cohorts.*

*The primary DLT observation period for cohorts that include Dose Prime will be 21 days following the first dose (C1D1). The dose escalation should a Dose Prime be instituted is depicted in Figure 2.*

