**Figure 2 Study Schematic Should Dose Prime Be Explored**

DL = Dose Level

\* In-patient observation applies to all cohorts

\*\* Dose level 1 will be higher than Dose Prime

\*\*\* Dose level 2 will be higher than Dose Level 1

*For cohorts instituting a Dose Prime, there will be a 72 hour observation period between the first dose administered to each of the initial patients enrolled (ie, patients contributing to initial DLT evaluation) at a new dose level. In addition to in-patient observation following the C1D1 dose, patients enrolled in cohorts instituting a Dose Prime must also undergo in-patient observation for at least 24 hours (for cohorts where PF-06671008 will be administered IV) or 48 hours (for cohorts where PF-06671008 will be administered SC) following the C1D8 dose.*

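### If a Dose Prime is used, the accumulation ratio as defined mixes the ratio of escalated to priming dose with true accumulation

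*SAP*

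**What the plan says.** The parameter table in SAP 5.3.4 has a row labelled "Observed accumulation ratio" whose formula is "AUC_{dose\ 4, \tau} / AUC_{dose\ 1, \tau": the AUC over one dosing interval after dose 4, divided by the same quantity after dose 1. Protocol 2.2 and 9.5.1 define Rac as the steady-state interval AUC over the single-dose interval AUC. No version contains the dose.

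On priming, protocol 3.2.1 describes "the inclusion of the fixed priming dose as the first dose (C1D1) followed by a second dose (C1D8) that will continue to be escalated", and SAP 2.2.2 repeats this. The legend to SAP Figure 2 adds: "Dose level 1 will be higher than Dose Prime". Dosing is weekly in 21-day cycles, so dose 4 falls on Cycle 2 Day 1. Protocol 3.1 keeps that link when Cycle 1 is delayed by toxicity: "the day when the patient receives their 4th dose of study drug will be counted as Day 1 of Cycle 2".

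On analysis, SAP 6.3.2 summarises each PK parameter, Rac included, descriptively by dose, cycle and day. Protocol 9.5.1 goes further: "The observed accumulation ratio and the linearity ratio will be summarized descriptively", followed by a log-scale one-way ANOVA with dose as the only term and back-transformed 90% confidence intervals. Dose normalisation is planned only for the plots of AUC and Cmax against dose (protocol 9.5.1, SAP 6.3.2).

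**The concern.** An AUC ratio with no dose term measures accumulation only when the two doses are equal. In a primed cohort they differ by design. Priming is the only within-patient escalation allowed, so every primed patient without a reduction has dose 4 above dose 1. The reported Rac then carries the dose step as well as the accumulation.

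Two consequences follow. First, the prime is fixed while the later dose goes up from cohort to cohort, so Rac climbs with dose even if PK is perfectly linear. That could be read as dose-dependent accumulation, both in the SAP's summaries by dose and in the protocol's ANOVA. Second, a primed patient's Rac spans two dose levels, and neither document says under which one it is filed. Primed and unprimed patients could therefore be pooled.

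The reverse error arises in an individual whose dose is reduced before dose 4.

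Rac is a listed secondary endpoint, and characterising single- and multiple-dose PK is a secondary objective of both Parts.

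**Working it through.** The documents state no numerical Rac, so there is no figure to reproduce. The check applies the SAP formula to a simple model.

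**Inputs from the documents**
- Dosing interval: 7 days.
- Dose 1: the priming dose. Doses 2 to 4: the escalated dose.
- Illustrative doses from the IV grid (SAP Table 1): a 100 ng/kg prime followed by 200, 300 or 400 ng/kg, so r = 2, 3 or 4. The choice of 100 ng/kg as prime is an assumption made for the arithmetic only.

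**Assumptions**
- Linear one-compartment PK with input short relative to the interval.
- Half-life 1 to 10 days, because the readable text gives none.

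**Formula as written.** Let q = exp(−ln2 × 7 / half-life), the fraction left after one interval. In units of the AUC after dose 1, the interval after dose 4 receives r from dose 4, rq from dose 3, rq² from dose 2 and q³ from the prime:

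Rac as written = r(1 + q + q²) + q³

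With equal doses (r = 1) this is 1 + q + q² + q³, the true accumulation to dose 4.

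| Half-life (days) | q | Equal doses | r = 2 | r = 3 | r = 4 |
|---|---|---|---|---|---|
| 1 | 0.008 | 1.01 | 2.02 | 3.02 | 4.03 |
| 2 | 0.088 | 1.10 | 2.19 | 3.29 | 4.39 |
| 4 | 0.297 | 1.41 | 2.80 | 4.18 | 5.57 |
| 7 | 0.500 | 1.88 | 3.62 | 5.38 | 7.12 |
| 10 | 0.616 | 2.23 | 4.22 | 6.22 | 8.21 |

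**Inflation factor.** This is [r(1 + q + q²) + q³] / (1 + q + q² + q³). It cannot exceed r, because the q³ term is not multiplied by r. At a 1-day half-life it is about 2, 3 and 4. At 10 days it is 4.22/2.23 = 1.9, 6.22/2.23 = 2.8 and 8.21/2.23 = 3.7.

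**Artificial dose trend.** At a 4-day half-life, true accumulation is 1.41 throughout. Rac as written reads 2.80, 4.18 and 5.57 at 200, 300 and 400 ng/kg.

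**Dose-normalised version.** Dividing each AUC by its dose gives 1 + q + q² + q³/r.

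| Half-life (days) | Equal doses | r = 2 | r = 4 |
|---|---|---|---|
| 1 | 1.01 | 1.01 | 1.01 |
| 2 | 1.10 | 1.10 | 1.10 |
| 4 | 1.41 | 1.40 | 1.39 |
| 7 | 1.88 | 1.81 | 1.78 |
| 10 | 2.23 | 2.11 | 2.05 |

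The dose ratio is removed. What remains is a small shortfall, because the lower prime leaves less carry-over: at r = 4 and 10 days, 2.05/2.23 = 0.92, or 8% low.

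**Reduction before dose 4.** The same arithmetic works with a ratio below 1. With negligible carry-over, one grid step down from 200 to 100 ng/kg gives 100/200 = 0.5 of the true value.

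**The case against.** The problem is conditional. Priming may or may not be instituted, and the documents qualify multiple-dose parameters by whether steady state is reached and the data permit. Unprimed cohorts without reductions are unaffected. All of that stands and limits the reach of the point.

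SAP 5.4.3 allows patients with events affecting PK to be excluded, and removes a known biased estimate in an individual subject from summaries. This gives the analyst a route for single patients with a reduced dose, although reduction is not named. It does not clearly cover a planned regimen applied to whole cohorts.

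Other outputs are sound: clearance has the dose in its formula, and the exposure plots against dose are normalised. The ANOVA appears only in the protocol, and the SAP, which may modify protocol plans, does not repeat it. The SAP's descriptive summaries by dose would still show the same trend.

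A reader might infer that Rac in primed cohorts simply equals the dose ratio, or that the inflation is exactly 2, 3 or 4. Neither holds in general. Rac is roughly the dose ratio times true accumulation, and those factors are upper limits approached at short half-life.

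A reader might also extend the point to the linearity ratio. The term appears only in protocol 9.5.1, without a formula, so the documents do not support any claim about it.

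Finally, parts of the PK schedule and SAP are redacted, and a rule there cannot be excluded.

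**Conclusion.** The point holds as a conditional one. If a Dose Prime is used, Rac as defined overstates accumulation in primed cohorts by a factor close to, and at most, the dose ratio, and it acquires a rise with dose that linear PK would not produce. For r = 2, 3 and 4 the factor runs from about 2, 3 and 4 down to about 1.9, 2.8 and 3.7 over assumed half-lives of 1 to 10 days. These sizes rest on linear one-compartment PK, an assumed half-life range and illustrative grid doses. A reduction before dose 4 biases an individual's Rac downward.

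No readable text normalises Rac, changes its reference dose or sets primed cohorts apart for it. The consequence is a misreported secondary PK endpoint. DLT, MTD and response analyses do not use it.

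**What to change.** In SAP 5.3.4, define Rac as (AUC over the interval after dose 4 / actual dose 4) divided by (AUC over the interval after dose 1 / actual dose 1). Equal-dose cohorts keep the same value, and patients reduced before dose 4 are also handled.

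In SAP 6.3.2, report Rac separately for primed and unprimed cohorts, as SAP 6.1 already does for subject counts, and state under which dose a primed patient is filed. If the protocol's ANOVA is run, keep the same separation.

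State two limits in the text. Normalisation assumes dose-proportional PK, which the plan still treats as something to explore. It also leaves the small downward difference shown above. The first escalated dose (Cycle 1 Day 8) is an alternative reference if sampling allows, with carry-over from the prime acknowledged; the visible schedules do not settle whether it does.

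The cost is one formula and a reporting rule, plus aligning the same definition in SAP 3.2, the protocol synopsis, protocol 2.2 and protocol 9.5.1. SAP 6.1 already derives the actual dose, so no new data are needed. No dose or clinical rule changes.
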